#### 14.2.1.2. Treatment Phases for Exacerbations

Treatment State	Definition
Pre-Treatment	
 
Exacerbation onset date < First dose of study treatment
 

On-Treatment	
 
First dose of study treatment ≤ exacerbation onset date ≤ Last dose of study treatment + 28 days
 
Any exacerbation with missing onset date will be assumed to be “On-Treatment”.
 
Any exacerbation with partial onset date will be assumed to be “On-Treatment” unless there is evidence to the contrary (e.g. month/year of onset is present and is earlier than the month/year of the first dose of study treatment).
 

Post-Treatment	
 
Exacerbation onset date > Last dose of study treatment + 28 days
 

Note: the first dose of study treatment will be defined as the earliest dosing date/time entered into the eCRF, regardless of whether self-administration of the injection was successful i.e. full dose administered for this dosing occasion.

### 14.3. Appendix 3: Data Handling Conventions

#### 14.3.1. Baseline Definition & Derivations

##### 14.3.1.1. Baseline Definitions

- Baseline will be defined for all subjects in the ‘All Subjects (Safety)’ population.
- The baseline values for each assessment will be the latest available assessment prior to administration of mepolizumab at Visit 2.

##### 14.3.1.2. Derivations and Handling of Missing Baseline Data

Definition	Reporting Details
Change from Baseline	= Post-Dose Visit Value – Baseline
% Change from Baseline	= 100 x [(Post-Dose Visit Value – Baseline) / Baseline]
Ratio to Baseline	= Visit Value / Baseline

##### NOTES :

- Unless otherwise specified, the baseline definitions specified in Section 14.3.1.1 will be used for derivations for endpoints / parameters and indicated on summaries and listings.
- Unless otherwise stated, if baseline data is missing no derivation will be performed and will be set to missing.

#### 14.3.2. Reporting Process & Standards

Reporting Process	
Software	

 
• The currently supported versions of SAS software will be used.
 
	
Reporting Area	
HARP Server	: uk1salx00175
HARP Area	: sb240563/mid204959
Analysis Datasets	

 
• Analysis Data Model (ADaM) datasets will be created according to Clinical Data Interchange Standards Consortium (CDISC) standards.
 
• For creation of ADaM datasets (ADCM/ADAE), the same version of dictionary datasets will be implemented for conversion from System Independent (SI) to Study Data Tabulation Model (SDTM).
 
	
Generation of RTF Files	

 
• Rich text format (RTF) files will be generated for the final reporting effort.
 
	

Reporting Standards	
General	

 
• The current GSK Integrated Data Standards Library (IDSL) will be applied for reporting, unless otherwise stated: 
 
○ 4.03 to 4.23: General Principles
 
○ 5.01 to 5.08: Principles Related to Data Listings
 
○ 6.01 to 6.11: Principles Related to Summary Tables
 
 
 
	

Reporting Standards	

 
○ 7.01 to 7.13: Principles Related to Graphics
 
○ Safety and study population displays will be based on the core IDSL templates for these data types.
 
	
Formats	

 
● The reported precision (decimal places [DPs]) will follow the IDSL statistical principles but may be adjusted to a clinically interpretable number of DPs.
 
	
Planned and Actual Time	

 
● Reporting for tables, figures and formal statistical analyses:             
 
● Planned time relative to dosing will be used in figures, summaries, statistical analyses and calculation of any derived parameters, unless otherwise stated.
 
● The impact of any major deviation from the planned assessment times and/or scheduled visit days on the analyses and interpretation of the results will be assessed as appropriate.
 
 
 
● Reporting for Data Listings:             
 
● Planned and actual time relative to study drug dosing will be shown in listings (Refer to IDSL Statistical Principle 5.05.1).
 
● Unscheduled or unplanned readings will be presented within the subject's listings.
 
● Visits outside the protocol defined time-windows (i.e. recorded as protocol deviations) will be included in listings.
 
 
 
	
Unscheduled Visits	

 
● Data recorded at an unscheduled visit will be re-assigned in the ADaM data sets to the closest nominal visit at which collection of data was scheduled, unless information already exists at that visit. Unscheduled data re-assigned to a scheduled visit will be reported in summary tables and figures. Unscheduled data that is not re-assigned to a scheduled visit will not be included in summary tables or figures by scheduled visit, with the exception of any unscheduled assessments of injection success which may be included in the summary of "best attempt" investigator assessment of self-administration of study treatment if appropriate – see Section 7.1. Unscheduled data that is not re-assigned to a scheduled visit will be considered in the derivation of baseline or highest/worst case post-baseline result for the summary tables.
 
● Data from all unscheduled visits will be included in listings and individual subject figures.
 
	
Early Withdrawal Visits	

 
● Data recorded at the early withdrawal visit will be re-assigned in the ADaM data sets to the next scheduled visit, unless information already exists at that visit. Early withdrawal data re-assigned to a scheduled visit will be reported at that visit in summary tables and figures. Early withdrawal visit data that is not re-assigned to a scheduled visit will not be included in summary tables or figures by scheduled visit. However early withdrawal data that is not re-assigned to a scheduled visit will be considered in the derivation of highest/worst case post-baseline result for the summary tables.
 
● Data from all early withdrawal visits will be included in listings and individual subject figures.
 
	
Descriptive Summary Statistics	
Continuous Data	Refer to IDSL Statistical Principle 6.06.1
Categorical Data	N, n, frequency, %
Reporting of Pharmacokinetic Concentration Data	
Descriptive	Refer to IDSL Statistical Principle 6.06.1

Reporting Standards	
Summary Statistics	Assign zero to non-quantifiable (NQ) values (Refer to GUI_51487 for further details)
Graphical Displays	

• Refer to IDSL Statistical Principals 7.01 to 7.13.

	

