- a. Pre-screening Visit (V0) can occur on the same day as the Screening Visit (V1) but must be completed prior to initiating any Visit 1 procedures; The Pre-screening Visit can be conducted up to a maximum of 2 weeks prior to the Screening Visit.
- b. The Early Withdrawal Visit will occur 4 weeks (±7 days) after last dose of mepolizumab for any subject who withdraws prior to Week 12
- c. Parasitic screening is only required in countries with high-risk or for subjects who have visited high-risk countries in the past 6 months. Sites should use local laboratories.
- d. Perform prior to mepolizumab administration during the study and prior to restarting pre-study mepolizumab treatment on study completion/early withdrawal.
- e. Subjects will be instructed to contact clinical study staff at any time if they have concerns or questions regarding self-administration. They will have the option of returning to the clinical site for further training or assistance with self-administration. Requirement for additional training or assistance will be documented.
- f. Self-administration of mepolizumab using the autoinjector should occur within 24 hours following the clinic visit.
- g. Includes measurement of eosinophil levels for pharmacodynamic analysis at Visits 2, 3, 4 and 5 (Week 0, 4, 8 and 12)
- h. Pharmacogenetic sample may be drawn any time after the respective informed consent form is signed and the subject is enrolled.
- i. Vital signs include temperature, sitting blood pressure, respiratory rate and pulse.

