**CONFIDENTIAL**

204959

No.	Population	IDSL / TST ID / Example Shell	Title	Programming Notes	Deliverable [Priority]
Safety : Figures					
11.34	All Subjects	AE1	Summary of On-Treatment Adverse Events Categorised as Malignancies		SAC
11.35	All Subjects	TAB_S1	Summary Profile of On-Treatment Adverse Events Categorised as Malignancies		SAC
11.36	All Subjects	AE1	Summary of On-Treatment Adverse Events Categorised as Opportunistic Infections		SAC
11.37	All Subjects	TAB_S1	Summary Profile of On-Treatment Adverse Events Categorised as Opportunistic Infections		SAC
Laboratory - Haematology					
11.38	All Subjects	LB1	Summary of Haematology Changes from Baseline by Visit	Include baseline values	SAC
11.39	All Subjects	LB3	Summary of Haematology Shifts from Baseline Relative to Normal Range by Visit		SAC
11.40	All Subjects	LB3	Summary of Haematology Shifts from Baseline Relative to PCI Criteria by Visit		SAC
Laboratory – Clinical Chemistry					
11.41	All Subjects	LB1	Summary of Clinical Chemistry Changes from Baseline by Visit	Include baseline values	SAC
11.42	All Subjects	LB3	Summary of Clinical Chemistry Shifts from Baseline Relative to Normal Range by Visit		SAC
11.43	All Subjects	LB3	Summary of Clinical Chemistry Shifts from Baseline Relative to PCI Criteria by Visit		SAC

No.	Population	IDSL / TST ID / Example Shell	Title	Programming Notes	Deliverable [Priority]
Safety : Figures					
ECG					
11.43	All Subjects	EG1	Summary of ECG Findings by Visit		SAC
11.45	All Subjects	EG2	Summary of ECG Values by Visit		SAC
11.46	All Subjects	EG2	Summary of Change from Baseline in ECG Values by Visit	Include baseline values	SAC
11.47	All Subjects	TAB_ECG1	Summary of Actual and Change From Baseline QTc(F) Values by Category (msec)	If there are unscheduled ECGs, include "Maximum Value Post Baseline" as an additional timepoint and add footnote: "Note: Maximum Value Post-Baseline includes scheduled and unscheduled assessments."	SAC
11.48	All Subjects	TAB_ECG1	Summary of Actual and Change From Baseline QTc(B) Values by Category (msec)	If there are unscheduled ECGs, include "Maximum Value Post Baseline" as an additional timepoint and add footnote: "Note: Maximum Value Post-Baseline includes scheduled and unscheduled assessments."	SAC

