**CONFIDENTIAL**

204959

Example TAB\_ECG1  
 Protocol: 204959  
 Population: All Subjects (Safety)

Page 1 of 1

Table X  
 Summary of Actual and Change from Baseline QTc(F) Values by Category (msec)

	Population	Liquid Autoinjector (N=XX)
Baseline	n	XX
	<=450	XX (XX%)
	>450 - <=480	XX (XX%)
	>480 - <=500	XX (XX%)
	>500	XX (XX%)
Week 12	n	XX
	<=450	XX (XX%)
	>450 - <=480	XX (XX%)
	>480 - <=500	XX (XX%)
	>500	XX (XX%)
Week 12 Change from Baseline	N	XX
	<-60	XX (XX%)
	>=-60 - <-30	XX (XX%)
	>=-30 - <0	XX (XX%)
	>=0 - <30	XX (XX%)
	>=30 - <60	XX (XX%)
	>=60	XX (XX%)

userid: /arenv/arprod/compound/study/final/drivers/drivername.sas DDMMYYYY HH:MM

Example LIST\_POP1  
Protocol: 204959  
Population: All Subjects (Safety)

Table X.X  
Listing of Baseline Mepolizumab Use

Treatment: Liquid Autoinjector

Site Id./ Unique Subject Id.	Subject Currently Receiving Treatment with Mepolizumab?	Blood Eosinophil Count Criteria Met [1]?	Most Recent Blood Eosinophil Count Prior to Starting Mepolizumab (cells/uL) [2]
XXXXXX/ MID204959.XXXXXX	Yes	Yes	300

[1] Blood eosinophil count immediately before starting mepolizumab that was  $\geq 150$  cells/uL or a blood eosinophil count that was  $\geq 300$  cells/uL in the 12 months prior to starting mepolizumab.  
[2] Historical value taken prior to starting mepolizumab for subjects currently receiving treatment with mepolizumab only.

userid: /arenv/arprod/compound/study/final/drivers/drivername.sas DDMMYYYY HH:MM

Example LIST\_POP2  
Protocol: 204959  
Population: All Subjects (Safety)

Table X.X  
Listing of Previous Mepolizumab Clinical Trials

Treatment: Liquid Autoinjector

Site Id./ Unique Subject Id.	Did the subject participate in a previous mepolizumab clinical trial?	Previous Protocol Identifier	Previous Subject Number
XXXXXX/ MID204959.XXXXXX	Yes	205667	XXX

userid: /arenv/arprod/compound/study/final/drivers/drivename.sas DDMMYYYY HH:MM

CONFIDENTIAL

204959

Example LIST\_INJ1  
 Protocol: 204959  
 Population: All Subjects (Safety)

Page 1 of 1

Table X.X  
 Listing of Investigator Assessment of Injection Success

Treatment: Liquid Autoinjector, Standard Label + Pictogram

Site Id./ Unique Subject Id.	Visit/ In-Clinic or Home Injection	Date of Assessment	Was Self- Administration of Injection Successful?	User Error	Device Error
XXXXXX/ MID204959.XXXXXX	WEEK 0/ IN-CLINIC	DDMMYYYY	Yes		
	WEEK 4/ HOME	DDMMYYYY	Yes		
	WEEK 8/ IN-CLINIC	DDMMYYYY	Yes		

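### Read literally, the early-withdrawal rule leaves subjects who stop after one or two doses without a row in the QTc category tables

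*SAP*

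**What the plan says.** Five places in the SAP bear on this.

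- **Early Withdrawal Visits (14.3.2).** "Data recorded at the early withdrawal visit will be re-assigned in the ADaM data sets to the next scheduled visit", with an exception only where that visit already holds information. The next sentence reads: "Early withdrawal data re-assigned to a scheduled visit will be reported at that visit in summary tables and figures". The worst-case provision is confined to data that stay where they are: "However early withdrawal data that is not re-assigned to a scheduled visit will be considered in the derivation of highest/worst case post-baseline result".
- **Unscheduled Visits (14.3.2, just above).** These data go to the "closest nominal visit at which collection of data was scheduled". That limit is missing from the early-withdrawal rule.
- **Schedule (14.1.1).** The 12-lead ECG is marked at Visit 1 and Visit 5 only. On the timing of the withdrawal visit: "The Early Withdrawal Visit will occur 4 weeks (±7 days) after last dose of mepolizumab for any subject who withdraws prior to Week 12".
- **QTc category displays (14.8.6, Tables 11.47 to 11.49; shell TAB_ECG1 in 14.9).** The shell has three blocks: Baseline, Week 12, and "Week 12 Change from Baseline". A maximum post-baseline timepoint is conditional; its programming note opens "If there are unscheduled ECGs, include".
- **Antibody displays (14.8.7; shell TAB_S2).** Antibody samples have the same post-dose timing as the ECG, and there the row pools Week 12 with Early Withdrawal.

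**The concern.** The early-withdrawal rule is written for all assessments at once. It works for laboratory tests, vital signs and PK, which are also planned at Weeks 4 and 8. It does not fit the ECG, whose only planned post-dose time is the end-of-study or withdrawal visit. A subject who leaves after one or two doses can have that ECG stored under a visit for which the QTc category tables have no row.

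Those tables are where a reader looks for how many subjects moved into a higher QTc band or had a notable increase. If early leavers are missing from the post-dose blocks, the blocks describe only subjects who reached Week 12 or withdrew after the third dose, and nothing in the table says so. Two programmers could also read the rule differently and produce different counts.

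**Working it through.** **1. The plan's own figure.** Protocol 9.2.1 assumes up to 5% dropout and wants 150 subjects with complete data. 150 / (1 − 0.05) = 157.9, rounded up to 158, which matches the planned enrolment. The implied number of dropouts is 158 − 150 = 8 (158 × 0.05 = 7.9), or 8 / 158 = 5.1%.

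**2. Where each early-withdrawal ECG goes.** Doses are at Weeks 0, 4 and 8, and the withdrawal visit is at last-dose week + 4, ±7 days. Days below are nominal, counted from the first dose.

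| Last dose | Withdrawal visit | Next scheduled visit | ECG planned there? | Post-dose row in Tables 11.47–11.49 |
|---|---|---|---|---|
| Week 0 | Week 4 (days 21–35) | Week 4 | No | None |
| Week 4 | Week 8 (days 49–63) | Week 8 | No | None |
| Week 8 | Week 12 (days 77–91) | Week 12 | Yes | Week 12 |

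A subject last dosed at Week 0 who still attended Visit 3 might map to Week 8 instead, which makes no difference here. The exception for existing information does not block the move, because no planned ECG exists at Week 4 or Week 8.

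**3. Whether another row picks these ECGs up.** The maximum post-baseline row would be expected to include them, since its footnote covers scheduled as well as unscheduled assessments. But it is produced only if unscheduled ECGs exist, and a planned withdrawal-visit ECG does not clearly meet that condition.

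**4. Whether another display shows them.**

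- Tables 11.43 (ECG findings), 11.45 (values) and 11.46 (change from baseline) are by visit, so the data could appear there under Week 4 or Week 8. They would be sparse rows for visits with no planned ECG.
- Listing 38 is the only ECG listing in the display list. It is limited to QTc above 500 msec or an increase of at least 60 msec.
- TAB_ECG1 also has bands for QTc above 450 to 480 msec, above 480 to 500 msec, and an increase of 30 to below 60 msec. An affected subject in one of these bands, and below the Listing 38 limits, would be in no category row (unless the maximum row is produced) and in no ECG listing.

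**5. Size.** Let k be the number who leave after dose 1 or 2 and have a withdrawal-visit ECG. If everyone else contributes at Week 12, that row has n = 158 − k:

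- k = 0: n = 158, none missing
- k = 4: n = 154, 4 / 158 = 2.5% missing
- k = 8: n = 150, 8 / 158 = 5.1% missing

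The last line requires every planned dropout to leave before the third dose and attend the withdrawal visit.

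**The case against.** The strongest reply is that the rule is ambiguous rather than wrong. In the schedule, End of Study and Early Withdrawal share one column labelled Week 12, which holds the only post-dose ECG mark, so for ECG the next scheduled visit could be taken to mean Week 12. That reading is possible. But the SAP does not state it, and the neighbouring rule for unscheduled visits shows how the limit is worded when it is intended. The ambiguity stands and is reason enough for a sentence.

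A second reply is that nothing is lost: the by-visit ECG tables can carry the data and Listing 38 catches extreme values. This is largely right and narrows the point to the category rows, mainly for intermediate values.

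A third concerns what a reader might infer, namely that the tables would hide subjects withdrawn because of their ECG. The documents do not support that. No ECG is planned between Visit 1 and Visit 5/Early Withdrawal, so a QTc withdrawal before Visit 4 would need an ECG outside the schedule, and an unscheduled ECG is what brings in the maximum row. Protocol 5.5.3 and 7.7.6 also call for two more ECGs after a prolonged QT. The SAP does not say how such repeats are labelled when taken within the withdrawal visit, so the trigger is plausible there but not assured. The clearer exposure is among subjects who leave for other reasons.

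Finally, TAB_ECG1 is an example shell, and pooling withdrawal ECGs under Week 12 mixes exposures. Both are fair. Neither removes the need to say where these ECGs are counted.

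**Conclusion.** The point holds as a gap in a stated rule. Followed literally, SAP 14.3.2 removes from Tables 11.47 to 11.49 the only planned post-dose ECG of subjects last dosed at Week 0 or Week 4, unless an unscheduled ECG happens to trigger the maximum row. Withdrawals after the third dose are handled correctly.

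The size is 0 to about 8 of 158 subjects (at most 5.1%), assuming dropout stays within the planned 5%. The upper end is a worst case, not an expectation.

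It would be tempting to say that a QTc above 500 msec in one early leaver would be reported as 0 of 150 instead of 1 of 158. At most this describes the Week 12 row. The same value would be in Listing 38, and probably in the maximum row if repeat ECGs are recorded as unscheduled.

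The study is descriptive, with no hypothesis test (protocol 9.1). The primary endpoint is untouched and no conclusion turns on this. It is a cheap improvement to a safety display.

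**What to change.** Three changes:

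1. In SAP 14.3.2, assign early-withdrawal data to the next visit at which that assessment is scheduled, matching the rule for unscheduled visits. Assessments planned at Weeks 4 and 8, such as laboratory tests, vital signs and PK, would map as they do now.
2. In TAB_ECG1, label the post-dose rows Week 12/Early Withdrawal, as TAB_S2 does for antibody results.
3. In Tables 11.47 to 11.49, always produce the maximum post-baseline row.

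The cost is one SAP sentence, a relabelled shell and an amended programming note, with no new data and no protocol amendment. The small downside is that the pooled row combines subjects with one, two and three doses, which a footnote giving the number of early withdrawals can make plain.

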**14.4. Appendix 4: Derived and Transformed Data**

**14.4.1. General**

Multiple Measurements at One Time Point

 
• May arise when unscheduled visits are re-assigned to a nominal visit (see Section 14.3.2). If there is data at the nominal visit, the nominal visit data will be used in the summary tables and figures, with the exception of any unscheduled assessments of injection success which may be included in the summary of “best attempt” investigator assessment of self-administration of study treatment if appropriate – see Section 7.1. All assessments will be listed.
 
• Subjects having both High and Low values for Normal Ranges at any post-baseline visits for safety parameters will be counted in both the High and Low categories of “Any visit post-baseline” row of related summary tables. This will also be applicable to relevant Potential Clinical Importance (PCI) summary tables.
 

Study Day

 
• Calculated as the number of days from the earliest dosing date/time entered into the eCRF, regardless of whether self-administration of the injection was successful i.e. full dose administered for this dosing occasion.             
 
• Ref Date = Missing → Study Day = Missing
 
• Ref Date < Visit 2 Date → Study Day = Ref Date – Visit 2 Date
 
• Ref Date ≥ Visit 2 Date → Study Day = Ref Date – (Visit 2 Date) + 1
 
 
 

**14.4.2. Study Population**

Demographics
Age

 
• GSK standard IDSL algorithms will be used for calculating age where birth day and month will be imputed ‘30th June’.
 
• Birth date will be presented in listings as ‘YYYY’.
 
• Age will be calculated relative to the date of the screening visit (Visit 1).
 

Body Mass Index (BMI)

 
• Calculated as Weight (kg) / [Height (m)]
 

Disease Duration

 
• Calculated in years as Number of Years + (Number of Months)/12
 

Extent of Exposure

 
• Number of months of exposure to liquid mepolizumab during this study will be calculated based on the formula:  Duration of Exposure (Months) = (Date of Last Dose of Study Treatment – Date of First Dose of Study Treatment + 29) × 12/365.25 
 
• The first dose of study treatment will be defined as the earliest dosing date/time entered into the eCRF, regardless of whether self-administration of the injection was successful i.e. full dose administered for this dosing occasion.
 

**14.4.3. Evaluation of Autoinjector**

Time from removal of autoinjector from storage to injection

 
Calculated in minutes as Time of Injection – Time Autoinjector Removed from Storage
 

**14.4.4. Safety**

Adverse Events
Drug Related AEs
AEs with relationship marked 'YES' or relationship missing.
AEs Leading to Permanent Discontinuation from Study Treatment or Withdrawal from the Study
AEs with action marked "Study treatment withdrawn" or withdrawn from study status marked "YES", or a response to either of these questions is missing.
AE Time Since First Dose (Days)

 
If AE start date < Date of first dose of study treatment then Time since first dose = AE start date - Date of first dose of study treatment
 
If AE start date ≥ Date of first dose of study treatment then Time since first dose = AE start date – Date of first dose of study treatment +1
 
Missing if AE start date or date of first dose of study treatment is missing.
 

AE Duration (Days)

 
AE end date – AE start date + 1
 
Missing if AE start date or end date is missing.
 

AESIs

 
See Section 11.1.1
 

